5.1.3. Part C: Post-Treatment Follow-Up Period

Patients who are not enrolled in the extension Study JADY will have a Follow-Up Visit (Visit 801) approximately 28 days after the last dose of study drug.

Patients who discontinue from the study prior to Week 52 for any reason will have an Early Termination Visit performed, including x-rays. The Early Termination Visit should be performed as soon as logistically possible because this visit includes assessment of safety. Infrequently, patient and investigator availability may be such that the Early Termination Visit and the Follow-up Visit may occur on or about the same date. In this instance, the visits may be combined and should occur approximately 28 days after the last dose of study drug. All activities required for the Early Termination Visit should be completed according to the schedule of assessments (Protocol Attachment 1).

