5.2. Determination of Sample Size

Approximately 288 patients (144 in baricitinib, 144 in placebo) will provide:

- 99% power to detect a difference between the baricitinib and placebo treatment groups in ACR20 response rate (60% versus 35%) at Week 12 based on a 2-sided chi-square test at a significance level of 0.05.

The sample size and power estimates were obtained using nQuery® Advisor 7.0.

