In addition to the LS means for each group, the within-group p-value, the standard deviation, minimum, median, and maximum will be displayed for continuous safety variables.

Data collected at early termination visits will be mapped to the next scheduled visit number for that patient.

The following is a description of the analysis groups planned for this study. Refer to Section 6.1.3 for the definitions of analysis populations used for the efficacy and safety analyses.

Analysis Groups for the Efficacy and Health Outcomes Data

Summaries of efficacy and health outcomes data for the Week 0 to Week 12 period, the Week 0 to Week 24 period with data up to rescue, and the Week 0 to Week 52 period with data up to rescue/switch will be presented according to the following treatment groups:

- Placebo: patients randomized to placebo excluding data obtained after the receipt of baricitinib 4 mg, either as rescue therapy or according to the protocol-designated switch to baricitinib 4 mg,
- Baricitinib 4 mg: patients randomized to baricitinib 4 mg excluding data obtained after the receipt of rescue therapy.

Summaries of efficacy and health outcomes data for patients who are rescued/switched will be presented according to the following treatment groups:

- Placebo (rescued): patients randomized to placebo who were rescued on or before Week 24,
- Placebo (switched, not rescued): patients switched to baricitinib from placebo at Week 24 and not rescued after the initiation of baricitinib,
- Placebo (switched, rescued): patients switched to baricitinib from placebo at Week 24 and rescued after initiation of baricitinib,
- Baricitinib (rescued): patients randomized to baricitinib who were rescued.

Analysis Groups for the Safety Data

Summaries of safety data for the Week 0 to Week 12 period and the Week 0 to Week 24 period with data up to rescue will be presented according to the following treatment groups:

- Baricitinib 4 mg: patients randomized to baricitinib excluding data obtained after the receipt of rescue therapy,
- Placebo: patients randomized to placebo using data obtained prior to the receipt of baricitinib as rescue therapy.

Summaries of safety data for the Week 0 to Week 52 period with data up to rescue/switch will be presented for baricitinib 4 mg for patients who were randomized to baricitinib excluding data obtained after receipt of rescue therapy.

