For data collected in the ePRO tablet related to efficacy assessments, unscheduled postbaseline visits that fall within the visit windows defined by Lilly will be summarized in the by-visit analyses if there is no scheduled visit available. That is, a +4-day window is applied to Visit 3 (Week 1) and Visit 4 (Week 2), and a +7-day window is applied to Visits 5 through 15 (Weeks 4 through 52) within the same treatment period (and while receiving the same treatment). For example, data should not be pulled across study periods for placebo group, and data cannot be pulled from postrescue visits to previous nonrescued visits. If there is more than 1 unscheduled visit within the defined visit window and no scheduled visit available, the unscheduled visit closest to the scheduled visit date will be used.

The baseline value for the safety analysis of the treatment period until rescue, protocol-defined switch, or end of study (if patients are not rescued to baricitinib 4 mg) is defined as the last non-missing measurement on or prior to the date of first study drug administration (expected at Week 0, Visit 2). The baseline value for the safety postrescue/switch period for patients randomized to placebo who are rescued/switched is defined as the last non-missing measurement obtained prior to initiation of the new treatment (baricitinib). The baseline value for the safety analyses of the postrescue period for patients randomized to baricitinib 4 mg who are rescued is the same as their treatment-period baseline. Postbaseline measurements for rescued/switched patients are collected after the rescue/switch visit through Week 52 (Visit 15) or an early discontinuation visit.

The baseline value for the efficacy analysis of the post-treatment follow-up period is defined as the last non-missing assessment at the time of Week 52 (Visit 15) or early discontinuation visit.

The baseline value for the safety analysis of the post-treatment follow-up period is defined as the last non-missing assessment on or prior to Week 52 (Visit 15) or early discontinuation visit.

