- (1) For a baricitinib-treated patient who did not require rescue therapy:
 - Missing data at Week 16 will be extrapolated from baseline and an early discontinuation visit prior to Week 16, if available.
 - Missing data at Week 24 will be extrapolated from baseline and the last available postbaseline value prior to Week 24.
 - Missing data at Week 52 will be extrapolated from baseline and the last available postbaseline value prior to Week 52, if available.
- (2) For a baricitinib- or placebo-treated patient who was rescued at Week 16:
 - Missing data at Weeks 24 or 52 will be extrapolated from baseline and Week 16.
- (3) For a placebo-treated patient who did not require rescue therapy:
 - Missing data at Week 16 will be extrapolated from baseline and an early discontinuation visit prior to Week 16, if available.

- Missing data at Week 24 will be extrapolated from baseline and the last available postbaseline value prior to Week 24.
- Missing data at Week 52 will be extrapolated from baseline and the last available postbaseline value at or prior to Week 24.

2. Other method: Last observation carried forward

A last-observation-carried-forward (LOCF) approach will also be used for the Week 24 analyses of mTSS, bone erosion scores, and joint space narrowing. Data observed at Week 24 will be analyzed according to randomized treatment group regardless of rescue status. Patients with missing data at Week 24, as a result of study discontinuation or unreadable x-rays, will have their data imputed by last postbaseline observation carried forward.

Details of the missing data imputation rules, methods for between-reader adjudication, score derivations, and other details for the bone erosion scores, joint space narrowing scores, and mTSS are provided in [Appendix 2](#) (van der Heijde Modified Total Sharp Score) and [Appendix 4](#).

[Table 6-1](#) summarizes the imputation techniques for the various endpoints.

Table 6-1 **Imputation Techniques for Various Efficacy and Safety Variables**

Endpoint	Imputation Method
ACR 20/50/70 responses, DAS28-hsCRP and DAS28-ESR LDA and remission, EULAR response criteria based on the 28-joint DAS, ACR/EULAR remission according to the Boolean-based definition, HAQ-DI improvement from baseline ≥ 0.22 and ≥ 0.3 , CDAI LDA and remission, and SDAI LDA and remission	NRI
JSN, bone erosion scores, and mTSS	Linear extrapolation method and LOCF
mTSS ≤ 0 , mTSS ≤ 0.5 , and mTSS \leq SDC	NRI
HAQ-DI, DAS28-hsCRP	mBOCF/mLOCF

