 - a. If at least three items are $\geq\chi\%$, then STOP – assign the patient as a responder for ACR χ .
 - b. If at least three items are $<\chi\%$, then STOP – assign the patient as a nonresponder for ACR χ .
 - c. If less than three items are $\geq\chi\%$, then STOP – assign ACR χ response as blank.

To calculate the ACRx response at post baseline visits up to Week 52 using NRI:

- Step 1: Calculate the % improvement at the visit for all seven parameters as described above.
- Step 2: If all seven parameters are missing at the visit, or if the patient discontinued from the study prior to reaching the visit, then STOP – assign the patient as a nonresponder for ACRx.
- Step 3: If at least one of the seven parameters is non-missing at the visit and the patient is still enrolled in the study, then use LOCF to fill in any missing values.
- Step 4: If TJC68 AND SJC66 are BOTH $\geq\chi\%$, then proceed to step 5. If both are nonmissing but one or both is $<\chi\%$, then STOP – assign the patient as a nonresponder for ACR χ . If either or both are missing, then STOP – assign the patient as a non-responder for ACR χ .
- Step 5: Consider the following five variables: PATPAIN, PATGA, PHYGA, HAQ, hsCRP.
 - o If three or more of the five items are non-missing, then:
 - If three or more of the five items are $\geq\chi\%$, then STOP – assign the patient as a responder for ACRx.
 - If less than three of those five items are $\geq\chi\%$, then STOP – assign the patient as a non-responder for ACRx.
 - o If three or more of the five items are missing, then STOP – assign the patient as a non-responder for ACRx.

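### The SAP assigns every early-termination record to the next scheduled visit with no time or on-treatment limit, which contradicts its own film rules and mistimes data mainly at Week 52

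*SAP*

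**What the plan says.** SAP 6.1 (General Considerations) gives one general rule: "Data collected at early termination visits will be mapped to the next scheduled visit number for that patient". Nothing there limits how early the record may be, requires the patient to be on drug, or ranks this rule against others.

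Other sections treat the same records differently:

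- **SAP 6.1.4.** A post-baseline film belongs to a visit if taken from 14 days before to 30 days after it. Extrapolation runs on the actual film date. An early-termination film is taken only if the last one is more than 12 weeks old.
- **SAP 6.3.2.** An early-termination film is a source for extrapolation: "Missing data at Week 16 will be extrapolated from baseline and an early discontinuation visit prior to Week 16, if available". At Week 52, a missing value in an unrescued baricitinib patient is extrapolated from baseline and the last earlier film. A placebo value is extrapolated from baseline and the last film at or before Week 24.
- **SAP 5.1.3.** Early termination and follow-up may occasionally fall together, and then "the visits may be combined and should occur approximately 28 days after the last dose of study drug". SAP 6.1.1 ends the treatment period on the date of the early discontinuation visit.
- **SAP 6.1.1.** Unscheduled tablet records are accepted up to 4 days (Weeks 1 and 2) or 7 days (later visits) after the planned date.
- **SAP 6.3.1 and Appendix 1.** Patients who discontinue are nonresponders from that time on. After an adverse event, mBOCF carries the baseline value forward. SAP 6.11.1 describes NRI more loosely, as applying where a patient's data are wholly missing.

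**The concern.** A record that carries a visit label is no longer missing at that visit, so the label can switch off the rule for missing data. For films, the mapping turns a value that 6.3.2 would scale up to Week 52 into an unscaled observation. It does so only on baricitinib, because placebo Week 52 values never use films after Week 24. If damage accrues over time, the error favours baricitinib.

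For clinical and laboratory data, the mapping places early values, and occasionally off-drug values, in analyses that take visits at face value: the MMRM and the by-visit tables. A patient who leaves because of an adverse event is set to baseline under mBOCF, yet could enter the MMRM as an observed Week 12 improvement. No stated rule keeps that record out.

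**Working it through.** **The plan's own figure.** SAP 5.2 claims "99% power to detect a difference between the baricitinib and placebo treatment groups in ACR20 response rate (60% versus 35%) at Week 12" with 144 per arm and a two-sided 0.05 chi-square test. The pooled rate is 0.475. The null SE is √(2 × 0.475 × 0.525/144) = 0.0589. The alternative SE is √[(0.60 × 0.40 + 0.35 × 0.65)/144] = 0.0570. Power = Φ[(0.25 − 1.96 × 0.0589)/0.0570] = 0.991. The figure is reproduced and is not in dispute.

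**How early a mapped record can be.** Nominal visit days are from protocol Attachment 1; the earliest record is the day after the previous visit.

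- Week 12: Day 57 for Day 84, 27 days early.
- Week 16: Day 99 for Day 112, 13 days early, which is inside the 14-day film window.
- Week 24: Day 141 for Day 168, 27 days early.
- Week 52: Day 281 for Day 365, 84 days early.

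**Week 52 films.** With linear progression from a baseline film near Day 0, the unscaled change divided by the extrapolated change is t/365.

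- Day 281: 77%, understated by 23%.
- Day 300: 82%, understated by 18%.
- Day 330: 90%, understated by 10%.
- Day 351 (the 14-day limit): 96%, understated by 4%.

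If the baseline film was taken 42 days before Day 0, the Day 281 ratio is (281 + 42)/(365 + 42) = 79%, so 23% is the upper end. A film is normally due at such a visit, since 281 − 168 = 113 days exceeds 12 weeks. The label also creates a jump. A Day 279 film maps to Week 40, which has no planned film, so Week 52 stays missing and the change is multiplied by 365/279 = 1.31. Two days later the multiplier is 1.

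**Which Week 52 analyses move.** Mean change is descriptive at Week 52, because the ANCOVA test in 6.16 is at Week 24. The responder analysis for change ≤0 does not move, since a positive multiplier leaves the sign unchanged. Thresholds of 0.5 and the smallest detectable change can move where linear extrapolation is used, as 6.16 says (Table 6-1 names NRI). For example, 0.6 × 0.77 = 0.46 crosses 0.5.

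**Week 24 films.** With a Week 16 film on Day 112, the longest gap to a film mapped to Week 24 is 167 − 112 = 55 days, under 12 weeks, so no film is taken. Only a missed Week 16 film opens this route. The understatement is then at most 1 − 141/168 = 16%.

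**How many patients.** The synopsis plans about 245 completers of 288, so 43 leave. Their timing is not given. Spread evenly over 365 days and equally by arm (assumed):

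- Mapped to Week 12: 43 × 28/365 = 3.3, or 1.65 per arm (1.1% of 144).
- Mapped to Week 24: also 3.3.
- Mapped to Week 52: 43 × 85/365 = 10, or 5 per arm.

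If those five progress at the arm's average rate, the baricitinib mean change at Week 52 is understated by at most 5/144 × 23% = 0.8%.

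**ACR20, if mapping did override NRI.** Assume leavers respond at 60% and 35%. The difference rises by 1.65 × (0.60 − 0.35)/144 = 0.3 points, or by 1.7 points with 10 leavers per arm. In the reverse case, where 60% and 35% already include these records and NRI removes them, power is 0.990 and 0.981 respectively.

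**The case against.** The strongest reply is that specific rules govern and the mapping sentence is only a default. Much of this stands.

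A reader might infer that patients leaving between Weeks 8 and 12 could be counted as ACR20 responders. The documents do not support that. NRI in 6.3.1 depends on discontinuation, not on missing data. Appendix 1 makes anyone who left before the visit a nonresponder, and fills gaps only under this condition: "If at least one of the seven parameters is non-missing at the visit and the patient is still enrolled in the study". Its observed-data version blanks such patients, and Appendix 2 has the same rule for the DAS28 binary endpoints. The looser sentence in 6.11.1 does not repeal any of this. Nor do the documents suggest that several per cent of an arm leave in those four weeks; even dropout implies about 1.1%.

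mBOCF is similar. Section 6.1 explains that baseline is carried forward after an adverse event despite any good efficacy values. For other leavers the last value is carried forward anyway, so mapping changes the result only if the visit falls after discontinuation. Diary endpoints have their own rule in 6.13.1.1.

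For films, the reply is that 6.1.4 and 6.3.2 would prevail. That is the sensible reading, but no text says so, and the sentence in 6.1 applies to all early-termination data. The MMRM and by-visit tables have no specific rule to fall back on. The MMRM is only a sensitivity model, and combined visits are described as infrequent.

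**Conclusion.** The concern holds for films at Week 52, for the MMRM and for by-visit summaries. It does not extend to the primary result. An unrescued baricitinib patient's Week 52 change can be understated by up to 23%, assuming linear progression and a baseline film near Day 0. The effect on the arm mean is small, at most 0.8% under even dropout and average progression; it would be larger if leavers progress faster or leave late. Clinical values can be 27 days early at Week 12 or 24, 84 days early at Week 52, or about 28 days off drug.

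The primary ACR20 and mBOCF analyses are largely protected, with a loose end in the wording of 6.11.1. Week 24 mTSS is exposed only after a missed Week 16 film. mTSS is exploratory, and general efficacy testing stops at Week 24 (6.11). This is a contradiction worth removing, with no threat to the trial's main conclusion. Dropout timing and response among leavers are assumptions.

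**What to change.** Replace the sentence in SAP 6.1 with four rules:

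1. An early-termination film is assigned to a scheduled visit only within the 6.1.4 window, from 14 days before to 30 days after. Otherwise it keeps its own date and serves only as a source for linear extrapolation.
2. Other early-termination data are assigned to the next visit only within a stated number of days before it, for example 7 days, or 4 days for Weeks 1 and 2. Otherwise they serve only for carry-forward. The 6.1.1 windows cannot be borrowed, because they run after the planned date and cover only unscheduled tablet data.
3. Data from a combined early-termination and follow-up visit, about 28 days after the last dose, are not mapped to an on-treatment visit.
4. Sections 6.3.1, 6.3.2 and Appendix 1 take precedence over the mapping, and 6.11.1 is reworded to match 6.3.1.

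The cost is SAP wording and one derivation rule. A few observed records leave the MMRM and the by-visit tables. Films up to 14 days early would still count unscaled, with an understatement of at most 4% at Week 52.

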6.1.2. Derived Data

- Age (year) = (number of months between informed consent date and July of birth year) / 12, and then truncated to a whole-year (integer) age

- Age group (<65 years old, \geq 65 years old)
- Body mass index (BMI) (kg/m^2) = Weight (kg)/(Height (cm)/100) 2
- Duration of RA from onset (years) = [(Date of informed consent – Date of RA onset) + 1] / 365.25

Date of RA onset is defined as the date when the patient had symptoms of RA. If year of onset is missing, duration of RA from onset will be set as missing. Otherwise, unknown month will be taken as January, and unknown day will be taken as 01. The duration of RA from onset will be rounded to 1 decimal place.

- Duration of RA from diagnosis (years) = [(Date of informed consent – Date of RA diagnosis) + 1] / 365.25

Date of RA diagnosis is defined as the date when the patient was diagnosed with RA. See Duration of RA from onset (years) for the handling of missing year/month/date.

- Duration from onset of RA (years): 0 to <1; \geq 1 to <5; \geq 5
- Change from baseline = postbaseline measurement at Visit x – baseline measurement
- Percentage change from baseline at Visit x:
 - $((\text{Postbaseline measurement at Visit x} - \text{baseline measurement}) / \text{baseline measurement}) \times 100$
- Baseline disease activity based on the DAS28 (calculated separately for DAS28-ESR and DAS28-hsCRP)
 - Low disease activity: DAS28 \leq 3.2,
 - Moderate disease activity: DAS28 >3.2 to \leq 5.1,
 - High disease activity: DAS28 >5.1

6.1.3. Analysis Populations

Modified Intent-to-Treat (mITT) Population: The mITT population will include all randomized patients who received at least 1 dose of study drug. The intention-to-treat principle remains preserved since the decision of whether or not to begin treatment could not be influenced by knowledge of the assigned treatment in this double-blind study. Patients will be analyzed according to the study drug to which they were randomized or assigned per protocol.

The efficacy and health outcomes analyses will be conducted on a mITT basis unless otherwise specified.

Analysis of structural progression (van der Heijde mTSS) will be conducted on a subset of the mITT population that includes all randomized patients who received at least 1 dose of the study drug and have non-missing baseline and at least 1 non-missing postbaseline measurement.

Per-Protocol (PP) Population: The PP population will include all mITT patients who are not deemed noncompliant with treatment in Part A, who do not have selected important protocol deviations (refer to Section 6.5 for more details) in Part A, and whose investigator site does not

have significant good clinical practice (GCP) issues that require a report to regulatory agencies (regardless of study part). Qualifications and identification of the specific selected important protocol deviations that result in exclusion from the PP subsets will be determined prior to unblinding.

Since the primary and secondary efficacy endpoint analyses plus mTSS will be repeated using the PP population at Week 12 only (except that mTSS will be analyzed at Week 24), time constraints will be applied to the important protocol deviations that exclude a patient from the per protocol analysis population. For example, for treatment non-compliance, only patients with <80% compliance rate in the first 12 week period will be excluded from the PP population.

Safety Population: The safety population is defined as all randomized patients who received at least 1 dose of study drug and who did not discontinue from the study for the reason 'Lost to Follow-up' at the first postbaseline visit. Patients will be analyzed according to the analysis groups defined in Section 6.1.

Safety analyses up to the end of Part B will be conducted on this safety population.

Follow-up Population: The follow-up population is defined as patients who entered the follow-up period.

Safety Follow-up Population: The safety follow-up population is defined as patients in the safety population who entered the follow-up period and who did not discontinue in the follow-up period for the reason 'Lost to Follow-up'.

6.1.4. *Handling of X-ray Data*

X-rays are scheduled at the following visits: Screening (Visit 1), Week 16 (Visit 9), Week 24 (Visit 11), and Week 52 (Visit 15). X-rays are obtained at an early termination only if the most recent x-ray was more than 12 weeks ago.

There may be instances in which the x-rays are obtained on a date different from the scheduled InForm visit date. Also, there may be instances in which the set of x-rays for a visit (2 hands/wrists, 2 feet) are split across dates, resulting from the need to re-acquire some images in the set. To maximize the use of the observed data and avoid imputation, the following rules will be applied in the analysis:

1. Postbaseline x-rays administered within 14 days prior to the scheduled InForm visit date, or within 30 days after the scheduled InForm visit date, will be associated with that respective InForm visit for analysis.
2. An x-ray set split across different dates will have the data combined as long as the images are collected within 30 days of each other. The earlier x-ray date will be considered to be the date of the x-ray set.

Any linear extrapolation will be based on the date of the x-ray set instead of the InForm visit date.

